#### **Day 29 (8 AM $\pm$ 3 days)**

- Determine survival status from EHR if available or contact the subject by phone call/digital media as acceptable to the institution.

If the subject is being discharged before Day 15, follow the procedures outlined in [Section 8.5](#).

### **9.5.1 Unscheduled Visits**

Unscheduled visits and tests to assess AEs/SAEs are permitted as needed providing the AE related to study drug or SAE onset occurs within two (2) weeks after the final study dose.

### **9.6 Compliance with Study Procedures**

The time at which study procedures are conducted should follow the protocol timelines as closely as possible. However, it is recognized in a clinical setting that protocol-specified timings may not occur exactly as specified in the protocol. Provided that activities are carried out within the identified windows it will not be necessary to file a protocol deviation. It is understood that some scheduled study assessments may not be able to be conducted if the subject is unable to return to the clinic after discharge due to COVID-19 restricted travel; it is also understood that crowded hospital conditions/lack of personnel may make it impossible to carry out all requested study procedures; this will not be counted as a protocol deviation. The Day 7 and 15 visits are to be conducted via telephone if the subject has been discharged from the hospital with lab draws for subjects in the brequinar treatment group as described in [Section 8.5](#).

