Investigational Product and Dosage	
Subjects will be randomized in a 1:2 ratio to either standard of care (SOC) alone, or SOC + brequinar.
 
Brequinar is available as 100 mg oral capsules. Five once daily doses of brequinar 100 mg are to be administered on Study Days 1 – 5 for those assigned to the SOC + brequinar group.

	Treatment assignment will be randomized, open label.
Primary Objective	
 
To determine the safety and tolerability of SOC and SOC plus brequinar in hospitalized COVID-19 subjects.
 

Secondary Objectives	
 
To determine the rates of/changes in clinical status measures listed through Day 15:                             
 
Hospitalization status
 
Duration of hospitalization
 
NEWS2 Score
 
 
 
Mortality through Day 29
 

Exploratory Objectives	
 
To determine the change in SARS-CoV-2 nasopharyngeal viral load through Day 15
 
To determine the change in inflammatory markers through Day 15
 
To determine the change in DHO levels through Day 15
 
To determine the change in brequinar concentration levels through Day 7
 

Design	
This will be a phase 1a randomized, open label, multi-center study with approximately 24 subjects. All subjects will receive SOC per institutional guidelines for treatment of patients with COVID-19 infection. In addition to SOC, the brequinar group will receive brequinar 100 mg once daily for 5 days.
 
Subjects will have a Screening Visit followed as soon as possible with Study Day 1 (Day 1 may take place on the same day if entry criteria data are available). Study procedures are presented in detail in the procedures section, see below. Subjects will be followed through Day 15. Mortality will be assessed at Day 29.
 
See below for instructions regarding hospital discharge prior to Day 15.
 
Hematology and chemistry results and study information such as NEWS2 criteria are to be collected using the available EHR data as much as possible to avoid extra procedures for the study.

Sample Size:	Approximately 24 subjects will be randomized to either standard of care or standard of care plus brequinar in a 1:2 ratio (approximately 8 assigned to standard of care and 16 subjects on brequinar).
Number of Sites:	1 - 8
Study Period:	An enrollment period of 3 months is expected.

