#### **Subjects in the Brequinar Treatment Group**

If the subject is in the brequinar treatment group and is being discharged prior to completing the study, ensure a hematology/chemistry sample is obtained prior to discharge on the day of discharge. The subject is to return to the research or out-patient facility for the Days 7 and 15 visits if able and permitted. If unable or not permitted to return to the research facility due to COVID-19 restrictions, the remaining visit activities except for the lab draw will be conducted by phone

PROTOCOL NUMBER: CCB-CRISIS-01  
PROTOCOL VERSION FINAL DATE: 10SEPT2020

Page 22 of 58

or other digital media. The lab draw will be performed by an outpatient laboratory at a designated facility. Lab draws for any outpatient visits for the Day 7 and 15 visits are limited to safety labs (hematology and chemistry). Additional outpatient laboratory or study visits are to be conducted as needed for follow up of adverse events including hematologic toxicities.

PROTOCOL NUMBER: CCB-CRISIS-01  
PROTOCOL VERSION FINAL DATE: 10SEPT2020

Page 23 of 58

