## **6 TRIAL ENDPOINTS**

### **6.1 Primary Endpoint**

- Safety/tolerability measured by rates of post randomization adverse events and hematology/chemistry safety labs.

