#### 8.4.2 Study-Level Stopping Criteria

Following assessment by the Data Safety Monitoring Board (DSMB, see [Section 10.9](#)), the study is to be stopped as shown below:

- If  $\geq 4$  subjects on the brequinar treatment arm develop the same Grade 3 or 4 adverse event or symptomatic laboratory abnormality
- If  $\geq 8$  subjects on the brequinar treatment arm develop any Grade 3 or 4 adverse event or symptomatic laboratory abnormality.

### 8.5 Hospital Discharge Prior to Study Day 15

Subjects discharged from the hospital prior to the Day 15 visit are to return to a research facility when feasible for the remaining study visits. All scheduled study assessments are to be completed at these visits when conducted at a research facility.

PROTOCOL NUMBER: CCB-CRISIS-01  
PROTOCOL VERSION FINAL DATE: 10SEPT2020

Page 30 of 58

For subjects in the brequinar treatment group discharged from the hospital prior to Day 5, the subject is to take home the remaining doses of brequinar for daily self-administration. All subjects (brequinar and SOC) should have the scheduled assessments, e.g. lab samples and the nasopharyngeal swab, on the day of discharge and enter these results on the appropriate EDC page. Following discharge, subjects are to return to the research or out-patient lab collection facility for the remaining study visits, if feasible. Out-patient lab results are to be entered into the EDC and reviewed by a member of the study team. It is important that every effort be made to have subjects return at least on Days 7 and 15, if feasible. Subjects in the brequinar group are to record brequinar dosing on the medication diary provided by the study team. The study team will arrange for the subject to return any unused study medication to the research facility.

For all subjects, if discharge occurs on Days 10, 11, or 12, ensure a hematology/chemistry sample has been obtained on the day of discharge and record these results on the appropriate EDC page. Following discharge, the subject is to return to the research or out-patient lab collection facility for the Day 15 visit, if feasible. Out-patient lab results are to be entered into the EDC and reviewed by a member of the study team.

If discharge occurs on Days 13, 14 or 15, complete the Day 15 Final Visit activities prior to discharge. No further visits are required unless follow up is needed for a study drug-related AE or an SAE; the Day 29 mortality assessment is still to take place.

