#### **Final Visit Day 15 (8 AM $\pm$ 2 days)**

- Review Progress Notes and the medication record to collect information for any adverse events or new concomitant medications since Day 7 (from EHR if subject still hospitalized, otherwise by phone or other digital media).
- Collect results for SOC hematology/chemistry from the EHR if subject still hospitalized.
- Collect inflammatory markers from EHR for those analyzed locally; collect samples for DHO and cytokine panel to be analyzed at the central laboratory if subject still hospitalized.
- Collect NEWS2 Assessments from the EHR.
- Collect nasopharyngeal viral load sample.
- Collect hospital status (hospitalized, hospitalized in ICU, discharged).

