## 10 ADVERSE EVENT REPORTING

An adverse event is any untoward medical occurrence in a patient or clinical trial subject administered a medicinal product and which does not necessarily have a causal relationship with this treatment. An AE can therefore be any unfavorable and unintended sign (including an abnormal laboratory finding), symptom, or disease temporally associated with the use of the medicinal product, **whether or not considered related to the medicinal product.**

Events that occur prior to informed consent will be entered as medical history; AEs that occur after informed consent will be entered on the AE form.

Subjects will be questioned and observed for evidence of AEs, whether or not judged by the Investigator or designated person to be related to study drug. All AEs will be documented in the subject's medical record and CRF. For any pre-existing condition or abnormal laboratory finding that changes in severity after dosing, this change should be recorded as an AE. New abnormal laboratory findings that are clinically significant are considered AEs.

All adverse events will be collected from the time of informed consent through Day 15. After Day 15, collect/record only Serious Adverse Events (SAEs) or those judged by the Investigator or designated person to be related to study drug. AE details are to be documented including start and stop date and times, whether continuous or intermittent, severity, any intervention utilized to correct the event (e.g., medication, surgery, or other therapy), outcome and the relationship to the study drug.

AEs identified in the protocol as critical to the evaluation of safety must be reported to the Sponsor by the Investigator according to the reporting requirements within the time periods specified in the protocol.

AEs determined by the Investigator to be related to study drug must be followed until resolution or until they are considered stable or for at least 30 days after discontinuation of study drug.

Any serious adverse events (SAEs) experienced after 30 days post the last dose of study drug should only be reported to the sponsor if the investigator suspects a causal relationship to the study drug.

Abnormal laboratory values or test results occurring after study enrollment constitute AEs only if they induce clinical signs or symptoms, are considered clinically significant, or require therapy.

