Subjects who are discharged from the hospital before Day 7 will have follow up contacts with study staff (phone calls or other digital media) on Days 7, 15 and 29. Early discharge subjects in the brequinar treatment group will also have samples for safety labs (hematology and chemistry) obtained either at the research facility or at an outpatient laboratory on Study Days  $7 \pm 2$  and  $15 \pm 2$ . The safety laboratory results are to be initially assessed in real time by the Principal Investigator or designated person and the Medical Monitor. Any study drug-related clinically significant out-of-range laboratories or study drug-related adverse events will be followed as needed until resolution or stable.

The in-hospital assessments and phone call visits will specifically ask about possible hematologic toxicity including any evidence of the list below. Early discharge subjects will be provided with a list of the following events in lay terms and will be instructed to call the research team if any of these events occur.

PROTOCOL NUMBER: CCB-CRISIS-01  
PROTOCOL VERSION FINAL DATE: 10SEPT2020

Page 45 of 58

- Ecchymosis/purpura/petechiae
- Epistaxis
- Hemoptysis
- Hematuria
- Gingival bleeding
- Prolonged bleeding time from needle sticks, abrasions or lacerations
- Hematemesis
- Rectal bleeding
- Blood in stool
- Any other unusual bleeding noted by the subject or caregiver

Any of these symptoms considered clinically significant will be recorded as an adverse event and must be followed until resolved or stable.

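### Section 8.5 asks for post-discharge safety labs in both arms, but Sections 3.9, 9.6 and 10.8 name brequinar only; two adverse-event rules also use dose-based anchors that SOC subjects lack

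*Protocol*

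**What the plan says.** All references are to the current protocol version, dated 10SEPT2020.

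Section 6.1 defines the primary endpoint as "Safety/tolerability measured by rates of post randomization adverse events and hematology/chemistry safety labs". Section 11 presents all results descriptively by group. The synopsis plans "approximately 8 assigned to standard of care and 16 subjects on brequinar".

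On labs after early discharge, the sections differ:

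- **Section 8.5** (repeated in the synopsis) covers both arms: "All subjects (brequinar and SOC) should have the scheduled assessments, e.g. lab samples and the nasopharyngeal swab, on the day of discharge". Subjects are asked back for the remaining visits, with particular effort for Days 7 and 15. Those who cannot return have the draw at a research facility or outpatient laboratory. Return and draw are both qualified by feasibility, and neither is limited by arm.
- **Section 9.6** makes Days 7 and 15 telephone visits "if the subject has been discharged from the hospital with lab draws for subjects in the brequinar treatment group", and refers to Section 8.5 for this.
- **Section 10.8** gives follow-up contacts to everyone discharged before Day 7, then adds labs for one arm: "Early discharge subjects in the brequinar treatment group will also have samples for safety labs (hematology and chemistry"), on Days 7 and 15, each ± 2 days.
- **Section 3.9**, under a heading for the brequinar group, requires a discharge-day sample and Day 7 and 15 draws. It has no parallel text for SOC.

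On adverse events, Section 10 states: "For any pre-existing condition or abnormal laboratory finding that changes in severity after dosing, this change should be recorded as an AE". Section 9.5.1 permits unscheduled visits for events with onset within two weeks of the last study dose.

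**The concern.** Safety labs are half of the primary endpoint, and the control arm exists to show what COVID-19 and its usual treatment do to those labs. An abnormality can be counted only where a sample is taken. If discharged brequinar subjects are sampled and discharged SOC subjects are not, the brequinar arm will tend to show more abnormalities even if the drug does nothing.

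The protocol would not reveal this. Section 5, Section 9.6 and the notes to the Schedule of Events all say that assessments missed after discharge, or when a visit is by telephone, are not protocol deviations. A site that followed Section 9.6 or 10.8 to the letter would create unequal testing with nothing on file to show it. Samples not drawn cannot be recovered at analysis.

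The dose-based anchors raise a smaller problem of the same kind. The endpoint counts events after randomization, but one recording rule and one visit window start from dosing, which has no meaning for an SOC subject.

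**Working it through.** **1. The plan's own figure.** 24 subjects at 1:2 gives 24/3 = 8 SOC and 2 × 24/3 = 16 brequinar, as stated. No power, alpha or effect size is given, and none is in dispute.

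**2. Outpatient safety draws called for when a subject is discharged before Day 7.**

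| Section followed | Brequinar | SOC |
|---|---|---|
| 9.6 and 10.8 | 2 (Days 7, 15) | 0 |
| 8.5 and synopsis | 2, if feasible | 2, if feasible |

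The two rows cannot both be the schedule. Section 9.6 cites Section 8.5, but Section 8.5 contains no brequinar-only rule. The visit mode conflicts as well: telephone in 9.6, return to a facility when feasible in 8.5.

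**3. Where the conflict comes from.** The 05JUNE2020 and 06JULY2020 synopses limit the early-discharge rules to the brequinar group. The 31JULY2020 version widened Section 8.5 and the synopsis to both arms but left Sections 3.9, 9.6 and 10.8 naming brequinar. That text persists in the current version, which points to incomplete editing.

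**4. Discharge-day sample.** The sentence in Section 8.5 covering both arms sits in a paragraph that opens with brequinar discharges before Day 5. Separate instructions follow for Days 10–12 and Days 13–15. Read narrowly, an SOC discharge on Days 5–9 has no named sample. Read generally, it has one. Section 9.5 also collects daily labs in both arms through Day 7 unless the clinician stops them, so the doubt falls mainly on Days 8–9.

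**5. Worst-case size.** The documents give neither input, so both are assumed:

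- p = true rate of a notable lab abnormality, equal in both arms and equal in discharged and hospitalised subjects; range 0.10 to 0.30.
- d = share of subjects discharged early; range 0.25 to 0.75.

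If every discharged brequinar subject is tested, no discharged SOC subject is, and untested subjects stay in the denominator, the observed rates are p and p(1 − d). The spurious excess is p − p(1 − d) = p × d. Expected abnormalities found after discharge are 16 × p × d in brequinar and 0 in SOC, against 8 × p × d in SOC under equal testing.

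| d | p | Excess p × d | Found, brequinar | Found, SOC untested | Found, SOC tested |
|---|---|---|---|---|---|
| 0.25 | 0.10 | 2.5 points | 0.4 | 0 | 0.2 |
| 0.50 | 0.20 | 10 points | 1.6 | 0 | 0.8 |
| 0.75 | 0.30 | 22.5 points | 3.6 | 0 | 1.8 |

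With the same draws in both arms the excess is 0 in every row.

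**6. Adverse-event anchors.** The worsening rule in Section 10 and the window in Section 9.5.1 both start from dosing. Against them stand rules without a dose anchor: events are recorded from consent, new clinically significant lab findings count as events, and the synopsis defines post-randomization events by onset after randomization.

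**The case against.** The strongest reply is that the controlling text already treats the arms alike. Section 5 (for discharge before Day 7), Section 9.5 and the Schedule of Events send the reader to Section 8.5 for early discharge, and Section 8.5 covers both arms. The Schedule's Day 15 hematology/chemistry entry has no arm limit. This stands, so a reader who infers that the protocol requires unequal testing throughout goes too far. It does not settle the matter. Three sections still say something else, Section 10.8 words the brequinar draws as definite while Section 8.5 makes draws conditional on feasibility, and a missed SOC sample leaves no deviation.

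Other inferences that the documents do not support:

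- **That worsening counts only after dosing.** Section 10 does not say so, and the consent- and randomization-based rules can still capture worsening in SOC subjects.
- **That the Day 15 line in Section 9.5 is an arm difference.** In "Collect results for SOC hematology/chemistry from the EHR if subject still hospitalized", SOC means standard-of-care results in the health record, for both arms. The condition limits that source.
- **That Section 3.9 cancels the swab and DHO samples.** "Lab draws for any outpatient visits for the Day 7 and 15 visits are limited to safety labs (hematology and chemistry") concerns draws at outpatient visits, whereas Section 8.5 asks for the full assessments at a research facility. The two can be read together.
- **That SOC ceases to be a usable reference.** The analyses are descriptive, and early-discharge subjects in both arms are contacted and asked about bleeding.

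The size is also open to challenge. Full brequinar testing and no SOC testing are extremes. If lab summaries used only tested subjects, the expected SOC rate would stay at p under the same assumptions. With 8 SOC subjects, the illustrated loss is 0.2 to 1.8 expected findings.

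**Conclusion.** The point holds as an unresolved contradiction. The protocol permits post-discharge safety labs to differ by arm on a component of the primary endpoint, and its deviation rules would hide this. The likely direction is toward apparent brequinar toxicity. The size cannot be known from the documents: 2.5 to 22.5 percentage points is a worst-case illustration resting on the assumed p and d, complete brequinar testing, no SOC testing after discharge, and untested subjects kept in the denominator. It is zero if sites follow Section 8.5 equally in both arms.

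The dose-based wording in Sections 10 and 9.5.1 is a defective anchor for a randomized comparison, not an exclusion of SOC events.

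**What to change.** 1. Reconcile Sections 3.9, 9.6 and 10.8 with Section 8.5, so that one discharge-day, Day 7 and Day 15 hematology/chemistry schedule applies to all randomised subjects. State one visit mode for both arms: facility or outpatient laboratory if feasible, otherwise telephone.
2. In Section 8.5, make clear that the discharge-day sample applies whatever the day of discharge.
3. In Section 9.5, have the Day 15 lab line point to Section 8.5 for discharged subjects; nothing more is needed there.
4. In Section 10, anchor the worsening rule to randomization. In Section 9.5.1, give SOC subjects an equivalent anchor that does not depend on a dose.

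The cost is wording, plus at most about 8 SOC subjects × 2 outpatient draws = 16 draws, which Section 8.5 already requests.

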### **9.7 Early Withdrawal from the Study**

A subject may withdraw from the study at any time for any reason or for one of the reasons listed below. The Sponsor or Investigator may also terminate a subject's study participation after discussion with the other party if it is believed it would be unsafe for the subject to continue in the study.

PROTOCOL NUMBER: CCB-CRISIS-01  
PROTOCOL VERSION FINAL DATE: 10SEPT2020

Page 38 of 58

Subjects must be withdrawn from the study if any of the following events occur:

- Significant protocol violation or non-compliance, either on the part of the subject or the investigator or other site personnel;
- Decision of the Investigator or Sponsor that removal is in the subject's best interest;
- Severe unrelated medical illness or complication;
- Safety reasons/ significant adverse event;
- Subject request (withdrawal of consent);
- Sponsor decision.

Collect/conduct all evaluations for subjects who withdraw from the study prior to completing the treatment period unless consent is withdrawn.

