### 8.3 Study Discontinuation

Subjects will remain in the study through at least Study Day 15 (or longer if needed to follow up study drug-related adverse events). Mortality is assessed via a phone call or other digital media at Day 29.

After treatment, participants will be monitored through at least Study Day 15 (or longer if needed to follow study drug-related AEs/SAEs). Participants may discontinue from the study by withdrawing consent at any time or for any reason as presented in [Section 9.7](#).

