### 8.4 Stopping Criteria

#### 8.4.1 Individual Stopping Criteria

- Participants who develop a Grade 3 symptomatic toxicity that is assessed by the investigator to be related to the study drug are to be permanently discontinued from study treatment.
- Participants who develop a Grade 4 symptomatic toxicity, regardless of relatedness to study drug, are to be permanently discontinued from study treatment.
- Subjects who develop Grade 3 or 4 toxicities are to be followed by re-evaluation every 2 days, as feasible, until the toxicity returns to  $\leq$  Grade 2 severity.

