### **11.1 Study Populations for Analysis**

All analyses will be based on the ITT population, which is defined as all randomized subjects.

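### Section 9.7 orders withdrawal from the study, not just from drug, for outcome-related events and does not assure follow-up to Day 15 and Day 29 for subjects withdrawn after about Day 5

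*Protocol*

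**What the plan says.** In the 10SEPT2020 protocol, Section 9.7 opens its list with "Subjects must be withdrawn from the study if any of the following events occur". Three of the listed events matter here:

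- "Safety reasons/ significant adverse event"
- "Severe unrelated medical illness or complication"
- "Significant protocol violation or non-compliance, either on the part of the subject or the investigator or other site personnel"

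The word significant is not defined. The section closes with one sentence on data retention: "Collect/conduct all evaluations for subjects who withdraw from the study prior to completing the treatment period unless consent is withdrawn". Section 9.5 gives the treatment period as up to 5 days, in both arms.

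Elsewhere the protocol takes a different line:

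- Section 8.4.1: subjects with a drug-related Grade 3 or any Grade 4 symptomatic toxicity "are to be permanently discontinued from study treatment". Grade 3 and 4 toxicities are re-evaluated every 2 days, as feasible, until Grade 2 or lower; Section 10.1 repeats this.
- Section 8.3: "Subjects will remain in the study through at least Study Day 15".
- Section 10: all adverse events are collected through Day 15, and drug-related ones are followed until resolved or stable, or for at least 30 days after drug is stopped.
- Section 11.1: "All analyses will be based on the ITT population, which is defined as all randomized subjects".
- Section 7.1: enrolment runs until about 24 subjects have completed the study. Section 8.5 defines completion as having assessments through Day 15.

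**The concern.** The order is mandatory, and it concerns the study rather than the drug. Two of the three triggers are bad outcomes, so any follow-up lost because of them is related to outcome by construction. The primary endpoint is post-randomisation adverse events and safety laboratory results, and mortality through Day 29 is a secondary endpoint. Both need observation after the triggering event.

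The trial is open-label, so the judgement that an event is significant, or that removal is in the subject's best interest, could differ between arms. An analysis of all randomised subjects would then contain missing outcomes that the protocol itself created. Because enrolment continues until about 24 subjects have completed, a subject who leaves before Day 15 is in effect replaced by one who stays.

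**Working it through.** **1. The texts side by side.** A subject with a Grade 4 symptomatic toxicity during dosing stops drug and keeps being re-evaluated under 8.4.1 and 10.1. If the same event counts as significant, 9.7 says the subject must leave the study. The protocol draws the distinction between drug and study elsewhere. Section 10.7 takes a pregnant subject off the treatment aspects only and continues safety follow-up. Section 8.5 says that the Day 29 mortality assessment still takes place after discharge on Days 13 to 15. Section 9.7 has no comparable statement.

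**2. What the retention sentence covers.** It applies to withdrawal before the treatment period is completed. Drug is given on Days 1 to 5, so the uncovered time is:

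- adverse event and laboratory follow-up: Days 6 to 15, that is 15 − 5 = 10 of 15 study days;
- mortality: Days 6 to 29, that is 29 − 5 = 24 of 29 study days.

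Even for withdrawals on Days 1 to 5, the sentence gives no end date for the evaluations.

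**3. Arm sizes.** Section 7.1 gives about 24 subjects at 1:2. 24 × 1/3 = 8 standard of care and 24 × 2/3 = 16 brequinar, which reproduces the stated figures. The protocol gives no withdrawal rate, death rate, power or effect size, so what follows shows sensitivity and is not a forecast.

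**4. Range for Day 29 mortality.** With k subjects of unknown vital status among n, the best case counts none of them as dead and the worst case counts all of them. The width of the range is k/n.

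| k unknown | Brequinar, n = 16 | Standard of care, n = 8 |
|---|---|---|
| 1 | 6.25 points | 12.5 points |
| 2 | 12.5 points | 25 points |
| 3 | 18.75 points | 37.5 points |
| 4 | 25 points | 50 points |

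**5. A worked case (assumed).** Suppose 2 of 16 brequinar subjects die, and both had been withdrawn earlier with their status lost.

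- Full follow-up: 2/16 = 12.5%, exact 95% CI 1.6% to 38.3%.
- Observed: 0/14 = 0%, exact 95% upper limit 1 − 0.025^(1/14) = 23.2%.

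The two deaths vanish from the estimate, and the upper limit falls from 38.3% to 23.2%.

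**The case against.** A reader might infer that the subjects with the worst outcomes simply leave the trial, or that someone withdrawn on Day 8 has no further assessments at all. The documents do not support either reading.

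- Section 9.7 itself requires evaluations for withdrawals during the treatment period unless consent is withdrawn. The drug-stopping bullets of 8.4.1 can act only while drug is being given, which is largely that same period, so the clash with 8.4.1 and the follow-up gap overlap little.
- The event that triggers withdrawal is already recorded, so that part of the primary endpoint is kept.
- The listed illness or complication must be unrelated. Worsening of COVID-19 itself, a likely route to death here, is not obviously covered by that item.
- Section 10.5 requires reports on a serious adverse event until its overall clinical outcome is known. Section 10 requires follow-up of drug-related events and has its own form for death from disease progression. Section 9.5 takes Day 29 survival from the health record where available.
- Section 8.3 refers to 9.7 for discontinuation, so its Day 15 statement does not stand alone.
- The trial is descriptive, and the handling of missing outcomes commonly belongs in the SAP.

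All of this stands and narrows the point. It does not remove it. None of the recovery provisions exempts withdrawn subjects, but none says that it applies to them. Non-serious, unrelated later events and scheduled laboratory tests have no such provision. Nor can an SAP recover outcomes that the protocol does not assure will be collected.

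It is also tempting to put a figure on the resulting bias in mortality. That would need withdrawal and death rates that the protocol does not give, together with the assumption that every such death is missed.

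**Conclusion.** The point holds in a limited form and should be fixed. As written, 9.7 mandates study withdrawal for outcome-related events and assures continued evaluation only for withdrawals before the treatment period ends. After about Day 5, what is at risk is later adverse events and laboratory results, resolution of the triggering event, Day 15 status and Day 29 survival. This is in tension with Sections 8.3, 8.4.1, 10, 10.1 and 11.1, and the completer-based enrolment target adds to it.

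The size is 6.25 points (brequinar) or 12.5 points (standard of care) of mortality range per subject of unknown vital status. This rests on the planned arm sizes of 16 and 8. How many subjects would be affected cannot be derived from the documents and may be small, because some outcomes can be recovered by other routes.

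**What to change.** Reconcile 9.7 with 8.3, 8.4.1, 10 and 10.1 so that stopping study drug and leaving the study are distinct. Leave the rules on when treatment is stopped as they are; this review takes no position on them. Replace the last sentence of 9.7 with:

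> Every randomised subject who has not withdrawn consent completes all scheduled assessments through Day 15 and the Day 29 survival assessment, whenever and for whatever reason study treatment or participation is changed; survival is taken from the EHR where permitted.

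Add that protocol violations are recorded and do not end follow-up.

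The cost is a few sentences in the next amendment. No new visits or procedures are needed, because these assessments are already scheduled for every subject.
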